### **Conclusion:**

This monitoring plan for the PKD ketogenic diet intervention study is designed to ensure participant safety and maintain data integrity throughout the study. Regular assessments, reporting mechanisms, and decision-making criteria are in place to address unanticipated problems and make informed decisions regarding study continuation or termination.

# **Adverse Event Monitoring**

An AE is defined as any untoward medical occurrence in an investigation participant following written informed consent that does not necessarily have a causal relationship with the study product. An AE can be any unfavorable or unintended sign (including an abnormal finding), symptom, or disease temporally associated with the use of an investigational product, whether or not related to the investigational product. This includes any occurrence that is new in onset or aggravated in severity or frequency from the baseline condition, or abnormal results of diagnostic procedures (including laboratory test abnormalities).

Some side effects or GI symptoms could occur as an outcome of these dietary interventions; side effects listed in the beverage tolerability questions and reported will not be categorized as AEs but recorded as study outcomes. Side effects, outside of what is expected as a result of study product consumption, reported by participants and judged by the Investigators as medically relevant events and related to study product will be recorded as AEs.

Events should be considered AEs if they:

- Result in discontinuation from the study,
- Require treatment or any other therapeutic intervention,
- Require further diagnostic evaluation (excluding a repetition of the same procedure to confirm the abnormality),

ď

• Are associated with clinical signs or symptoms judged by the Investigator to have a significant clinical impact.

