The ketogenic diet intervention will start after all baseline testing is complete. Each participant may require slightly different levels of coaching depending on their baseline knowledge and individual situation. Thus, the intensity of engagement may vary across participants. The ketogenic diet will follow general principles with the aim to achieve blood ketones >0.5 mM, which will require most participants to consume <50 g/day carbohydrate and ~1.5 g/kg reference weight protein. Fat will comprise the remaining calories with an emphasis on monounsaturated and saturated sources from whole foods. A wide range of foods will be incorporated including non-starchy vegetables, fruits (berries, olives, tomatoes, lemons/limes), meats (beef, chicken, pork, fish, lamb), nuts and seeds, oils (olive, canola, coconut), cheese, butter, cream, eggs, and fatty fish (salmon, sardines). Nutritional ketosis is associated with natriuresis that will lead to sodium and fluid loss if the extra sodium excreted is not compensated by individualized intakes. If untreated, the resultant hypovolemia can manifest in side effects and adrenal stress (often mis-characterized as 'keto-flu') that disrupts body fluid, electrolyte, and mineral status. Thus, slightly higher sodium and potassium intakes are required to offset the natriuresis, which will be achieved through the provision of broth/LMNT electrolyte packs and appropriate food sources and cooking methods.

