#### DATA ANALYSIS AND STATISTICAL METHODS

The study will focus on percent change for TKV, albuminuria, and GFR pre and post the ketogenic dietary intervention. We will collect the following data for each patient including age, sex, race, baseline medications, BMI, albuminuria, GFR, and blood pressure. The univariate analysis will include the above variables and use analysis of variance to assess changes at baseline and at 12 months. Based on the univariate analysis, we will perform linear regression. Ketogenic diet administration will be forced into the model. Other variables will be chosen based on strength of the univariate analysis. Our outcome of interest will be percent change in TKV, albuminuria, and GFR. In regard to MR Imagining, we will utilize a statistical method to account for observer variability. Statistical techniques such as intra-class correlation coefficients (ICC) can quantify the level of agreement between different observers and help correct for any bias.

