#### **Decisions and Actions:**

**Data Review Meetings:** The study team will conduct regular data review meetings to assess the safety and progress of participants. This will involve a review of adverse events, dietary adherence, and MRI results.

**Stopping Criteria:** The study will include predefined stopping criteria to protect participant safety. If severe adverse events related to the ketogenic diet occur or if there is a significant worsening of kidney function, the study may be halted early.

**Reporting:** All monitoring findings, decisions, and actions will be documented in a monitoring report. Serious adverse events will be promptly reported to the Institutional Review Board (IRB) and relevant regulatory authorities, as required. Detailed Adverse enevt monitoring can be found below.

**Participant Withdrawal:** If participants wish to withdraw from the study, they will be allowed to do so at any time without prejudice.

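### The adverse event rules conflict, and expected diet side effects are routed to an unnamed beverage questionnaire and an unlisted outcome, so their recording is not assured

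*Protocol*

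**What the plan says.** Adverse Event Monitoring contains four rules in sequence.

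1. The opening definition is broad: an adverse event is any unfavourable occurrence after consent, and it "does not necessarily have a causal relationship with the study product".
2. The next paragraph anticipates side effects, including gastrointestinal symptoms, from the dietary interventions, and says that "side effects listed in the beverage tolerability questions and reported will not be categorized as AEs but recorded as study outcomes".
3. It then names the side effects that will be recorded as adverse events: "Side effects, outside of what is expected as a result of study product consumption", provided they are also judged medically relevant and related to the study product.
4. A list of four criteria follows. An event should be considered an adverse event if it meets, for example, "Result in discontinuation from the study" or "Require treatment or any other therapeutic intervention". The other two are further diagnostic evaluation and significant clinical impact in the investigator's judgment.

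Safety and Adverse Events via MRI gives a fifth rule: illness, signs or symptoms that get worse during the study are adverse events. It makes no exception for expected effects.

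Description of Ketogenic Diet names effects that the protocol foresees. It describes sodium and fluid loss and says "If untreated, the resultant hypovolemia can manifest in side effects and adrenal stress", with keto-flu as the common name for the result.

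**The concern.** A classification rule must let two people sort the same event in the same way. Here it does not, and the events affected are the ones the protocol itself predicts for this diet.

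Grading, the relatedness judgment, and recording with follow-up of events still open at the last visit all apply to adverse events. So does one of the two triggers in the stopping text, which begins "If severe adverse events related to the ketogenic diet occur". An expected effect that is not classed as an adverse event has a textual basis for being left out of each of these.

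The study has one arm and 20 participants, and its title puts feasibility first. How well the diet is tolerated is therefore one of the main things it can report, and there is no control arm in which the same under-recording would show.

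**Working it through.** No arithmetic applies, because the protocol gives no figure on this point. The check sets the sections side by side.

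**Step 1: does the questionnaire have a place in the trial?** The synopsis describes a single-arm dietary intervention. The nearest thing to a beverage is the broth and electrolyte packs in Description of Ketogenic Diet, which are supportive and are not called a study product. Table 1 and the visit lists under Study Procedures name no tolerability form. They contain a medical history questionnaire, and the text after Visit 6 mentions surveys without naming them.

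**Step 2: does the destination outcome exist?** The synopsis, Outcomes, Research Strategy, and Data Analysis and Statistical Methods cover kidney volume, cyst and fibrosis measures, albuminuria, GFR, and body mass and composition. The analysis section says "Our outcome of interest will be percent change in TKV, albuminuria, and GFR". None lists side effects or tolerability.

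**Step 3: what does each rule do with the same event?** I read the four criteria as alternatives, since the joining word is not legible in the text at hand.

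| Rule | Expected mild symptom, meets none of the four criteria | Expected severe symptom that needs treatment |
|---|---|---|
| Opening definition | Adverse event | Adverse event |
| Questionnaire exclusion | Not one if listed; list not given | Not one if listed; list not given |
| Unexpected, relevant and related | Not one, by implication | Not one, by implication |
| Four criteria | Not made one | Adverse event |
| MRI safety section | Adverse event if it worsened during the study | Adverse event if it worsened during the study |

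In both columns the rules disagree, and no sentence says which prevails.

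**Step 4: does the exclusion depend on the missing list?** Not entirely. A list that nobody can see may exclude nothing, but the third rule stands without it. It filters on whether an effect was expected and sets no severity limit. It also requires relatedness, which the opening definition does not.

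**Step 5: which way does the error run?** Taking the opening definition as the reference, the second and third rules can only remove events. Reported tolerability can only look better as a result.

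**Step 6: is the wording isolated?** No. The relatedness scale, Serious Adverse Event Follow-Up, and Withdrawal of Participants from the Study also refer to a study beverage. Read literally, relatedness is judged against something the trial does not give.

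**The case against.** The best defence is that the section can be read in a workable order: minor expected symptoms are set aside by default, and the four criteria then bring back anything of consequence. Those criteria have no exception for expected effects, and neither does the MRI safety definition. Tailored Sodium Adjustment calls for continuing watch for keto-flu, and the monitoring plan lists side effects among the safety information to be evaluated. These points stand and limit the finding. They do not remove it: the order of precedence is not written, and the monitoring sections name no form, grade or outcome.

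Four stronger readings are tempting, and the protocol does not support them.

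- A reader might infer that the likely harms of the diet are recorded nowhere. The four criteria, the MRI safety definition and the monitoring provisions rule that out.
- A reader might infer that only unexpected effects can trigger the stopping text. Expected effects that are adverse events under the four criteria or the MRI safety section also qualify, and worsening kidney function is a separate trigger.
- A reader might want a count of missing events. The protocol gives no incidence, so any percentage applied to 20 participants would be invented.
- A reader might conclude that no tolerability form is used. The unnamed surveys could include one, so the supportable statement is that none is named or scheduled.

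Hypovolemia is also described as conditional on sodium loss going uncompensated. Whether it counts as expected is an inference; for gastrointestinal symptoms the adverse event section itself anticipates them.

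**Conclusion.** The point holds as an internal inconsistency with a practical consequence. The protocol gives conflicting tests for an adverse event, and it sends a class of expected side effects to an instrument and an outcome that it does not define. The firm gap is expected symptoms that meet none of the four criteria. For more severe expected events the finding is that they can be classified either way, not that they are lost.

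The reach is all 20 participants over 12 months. The number of events affected is unknown. The conclusion assumes that the third rule excludes expected effects by implication, which is its natural reading beside the sentence before it. It also assumes that no document outside the protocol overrides the protocol's own classification rule. The change should be made before safety data are collected, because unrecorded symptoms cannot be reliably recovered afterwards.

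**What to change.** - Keep one adverse event definition and use it in both Adverse Event Monitoring and Safety and Adverse Events via MRI.
- Delete the filter on expectedness, or state that the four criteria override it.
- Record the remaining expected diet symptoms on a named checklist within the daily RedCap or Qualtrics entry that participants already complete, and report them as a tolerability outcome.
- Replace the beverage wording with the diet intervention in Adverse Event Monitoring, Relationship, Serious Adverse Event Follow-Up, and Withdrawal of Participants from the Study.
- Reconcile Decisions and Actions with Adverse Event Monitoring on whether expected events are adverse events for the stopping criterion. Which way that is settled is for the investigators.

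The cost is protocol wording and a few items on an existing form, with no change to design or sample size. The downside is a longer and less favourable adverse event table.

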#### **Grading and Severity**

The Investigator will evaluate all AEs with respect to their severity, and record the outcome and action taken on the AE study documents. AEs will be graded as:

Mild: Awareness of symptoms but easily tolerated

**Moderate**: Discomfort enough to interfere with but not prevent daily activity

**Severe:** Unable to perform usual activity

#### Relationship

The Investigator will also judge the likelihood that the AE was related to the study beverage and document this on the appropriate study documents as:

NOT RELATED	This category applies to those adverse experiences which, after careful consideration, are clearly and incontrovertibly due to extraneous causes (disease, environment, etc.).
UNLIKELY	In general, this category can be considered applicable to those experiences that after careful medical consideration at the time they are evaluated, are judged to be, unlikely related to the study beverage.

POSSIBLY	This category applies to those adverse experiences for which, after careful medical consideration at the time they are evaluated, a connection with the study beverage administration appears possible but cannot be ruled out with certainty.
PROBABLY	This category applies to those adverse experiences that, after careful medical consideration at the time they are evaluated, are felt with a high degree of certainty to be related to the study beverage.
DEFINITELY	This category applies to those adverse experiences which, the Investigator feels are incontrovertibly related to the study beverage.

Appropriate therapeutic action and follow-up measures will be performed by the Investigator in accordance with appropriate medical practice standard of care.

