# RESEARCH STRATEGY

This is a prospective study to determine ketogenic diet effect on htTKV, GFR, microalbuminuria. This is a single-center study of 20 patients with ADPKD and deemed high risk for progression to ESRD. This determined by combination of features of ADPKD and htTKV as assessed by prior computed tomography (CT) or MRI. Patients will be recruited from the Polycystic Kidney Disease (PKD) Clinic at Ohio State University Wexner Medical Center. Enrolled patients will have MRI for htTKV, urinary studies, blood tests at baseline, 6 months, and 52 weeks. Blood for GFR will be assessed three times over the course of the study including baseline, 6 months, and 1 year. Participants will follow ketogenic diet for 52 weeks. The [name] Lab Nutrition Team will manage the ketogenic diet.

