#### **Timing of Monitoring:**

# Monitoring will be conducted at the following time points:

**Baseline:** Prior to enrollment, each participant's medical history, kidney function, and MRI scans will be assessed.

**Regular Intervals:** During the study, participants will be monitored regularly. This includes assessments of dietary adherence (weekly by Key Personnel), vital signs, anthropometrics, blood work and glomerular filtration rate (GFR) will be used for monitoring disease progression at the specified intermediate time points (Baseline, Week 6 and Month 3, Month 6, Month 9, Month 12), and kidney function (Baseline, Month 12 via MRI).

**Adverse Event Reporting:** Any adverse events related to the ketogenic diet or the study protocol will be monitored continuously and reported promptly.

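### The only graded causality scale rates adverse events against a study beverage that this ketogenic-diet trial does not define, and the protocol's definitions of an adverse event disagree

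*Protocol*

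**What the plan says.** Research Strategy gives the intervention: "Participants will follow ketogenic diet for 52 weeks". The only drinkable supplies named are in Description of Ketogenic Diet, which mentions "the provision of broth/LMNT electrolyte packs" to offset sodium loss. The protocol never calls these a study beverage or a study product.

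Two safety rules turn on the diet. Timing of Monitoring states: "Any adverse events related to the ketogenic diet or the study protocol will be monitored continuously and reported promptly". The stopping criteria in Decisions and Actions allow the study to be halted "If severe adverse events related to the ketogenic diet occur", or if kidney function worsens significantly.

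The causality scale, under Relationship, asks a different question: "The Investigator will also judge the likelihood that the AE was related to the study beverage". Its grades follow suit; the middle one, for example, applies when "a connection with the study beverage administration appears possible but cannot be ruled out with certainty".

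On what counts as an AE, Adverse Event Monitoring opens with a broad definition that needs no causal link and includes laboratory abnormalities. Its second paragraph concedes that "Some side effects or GI symptoms could occur as an outcome of these dietary interventions" and then says that "side effects listed in the beverage tolerability questions and reported will not be categorized as AEs but recorded as study outcomes". Safety and Adverse Events via MRI gives another definition, based on worsening over the study.

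**The concern.** In a single-arm study of 20 patients there is no control event rate, so the investigator's attribution is the main way to separate effects of the diet from the course of the disease. If the attribution form names something that is not in the trial, two careful investigators can record the same diet-related event differently. One finds no beverage to blame and grades it unlikely; the other reads the beverage as the diet and grades it definite. The recorded grade would then be a poor basis for the diet-related reporting and halting rules.

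The AE definition raises a second question, namely which events enter the count at all. If the paragraphs disagree, the AE tally depends on which of them the person completing the form had in mind.

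**Working it through.** No calculation applies. The check sets the passages side by side and counts the wording in the protocol text at hand.

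**1. Extent of the beverage wording**

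- The word *beverage* occurs once in Adverse Event Monitoring (opening text), five times in Relationship, once in Serious Adverse Event Follow-Up and once in Withdrawal of Participants: 1 + 5 + 1 + 1 = 8. It does not occur anywhere before Adverse Event Monitoring, where the intervention is described.
- Grades that name it: unlikely, possibly, probably and definitely, so 4 of 5. Not related does not name it, but the lead-in governs all five.
- From Adverse Event Monitoring to Serious Adverse Event Follow-Up there are three undefined product terms: beverage 7, study product 3, investigational product 2, so 7 + 3 + 2 = 12 uses. The ketogenic diet is named 0 times there; the one reference to diet is to dietary interventions in general.

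**2. Question asked against question recorded**

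| Place | Object of relatedness |
|---|---|
| Timing of Monitoring (prompt reporting) | ketogenic diet or study protocol |
| Decisions and Actions (halting) | ketogenic diet |
| Relationship (graded scale) | study beverage |
| Serious Adverse Event Follow-Up (last exit) | study beverage, or study conduct |
| Safety and Adverse Events via MRI (laboratory tests) | ketogenic diet, yes or no, ungraded |

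The scale does not match the two rules that need its answer. The only attribution that names the diet is the yes/no judgement for laboratory tests.

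**3. SAE follow-up**

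Ongoing SAEs are followed until one of several exits is met. The last is attribution to something other than the beverage, or other than the study conduct. Because the two parts are joined by *or*, an SAE attributed to the diet could be read as meeting the first part. That is one reading of an ambiguous sentence.

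**4. AE definition**

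| Event | Adverse Event Monitoring, paragraph 1 | Same section, paragraph 2 | Safety and Adverse Events via MRI |
|---|---|---|---|
| Laboratory abnormality, not attributed to the diet, no consequences | AE | does not address it | not among the laboratory findings described as AEs |
| New symptom that does not then worsen | AE (new onset or aggravated) | as a side effect, an AE if unexpected, medically relevant and related | not clearly covered; the text speaks only of worsening |
| Worsening symptom on the tolerability list | AE | not an AE; kept as a study outcome | AE |

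So paragraph 1 asks for no causality, while paragraph 2 requires relatedness for side effects and removes the listed ones. The MRI section differs again on new onset and on laboratory findings. The tolerability questions behind the exclusion are not identified in the table of procedures or in the visit descriptions.

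**The case against.** The strongest reply is that this is a leftover word with an obvious meaning. Decisions and Actions, within the ketogenic-diet monitoring plan, sends the reader onward for the detailed AE procedure, so that procedure is adopted for the diet. The not-related grade covers only extraneous causes such as disease or environment, which does not naturally include the assigned diet. With no beverage in the trial, most investigators would substitute the intervention. This stands, and it limits the consequence. A reader might infer that relatedness to the diet is never graded; that holds only on a literal reading.

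Little safety action depends on the graded score. The SAE criteria and IRB notification carry no relatedness condition. The halting rule is discretionary and has a kidney-function trigger that needs no attribution, and Early Termination works from serum creatinine. The reporting instructions for SAEs also ask for follow-up information to be obtained promptly, which tells against the narrow reading of the last follow-up exit. All of this stands.

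On definitions, the laboratory sentences in the MRI section contain no *only if*, so they do not expressly exclude what the broader definition includes. The four-item list at the end of the Adverse Event Monitoring text would still bring in clinically significant events, and listed side effects are kept as study outcomes. Surveys are mentioned for the laboratory visits, so the tolerability questions may exist there. The point is therefore that they are not identified, not that they are absent.

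The objection does not remove the mismatch in the operative text. The form would record an answer about an undefined object, and the conflict between the first two paragraphs of Adverse Event Monitoring does not depend on how *beverage* is read.

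**Conclusion.** The protocol is wrong as written on this point and should be corrected. The causality scale, the AE exclusion, the last SAE follow-up exit and a withdrawal ground all refer to a beverage that the trial does not define, while the reporting and halting rules refer to the diet. The AE definition conflicts within its own section and with the MRI section.

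The size is moderate: ambiguous attribution and inconsistent AE counts. How many events would be affected cannot be computed; the counts above show how far the wording spreads, not its effect.

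Stronger readings are not supported. A reader might infer that diet-related harm would go unrecorded or that SAEs would go unreported. The reporting rules that need no relatedness, and the places that do name the diet, speak against that. A reader might also infer that the withdrawal wording prevents removal of a participant. It does not, since undue risk and medical reasons are separate grounds there. The conclusion assumes that the AE form, which is not shown, follows the protocol's wording.

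**What to change.** - In Relationship, rate each AE for its relationship to the ketogenic diet, including supplied foods and electrolytes, and separately to study procedures.
- Replace the beverage and product terms in Adverse Event Monitoring, Serious Adverse Event Follow-Up and Withdrawal of Participants with the actual intervention, so that the follow-up exit and the withdrawal ground are reconciled with the diet.
- Reconcile Adverse Event Monitoring and Safety and Adverse Events via MRI to one causality-free AE definition. The first paragraph of Adverse Event Monitoring already provides one. Record relatedness as a separate field.
- Identify the tolerability questions and the visits at which they are asked, or remove the reference.

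The cost is a wording amendment and an edit to the AE form. The downside is that somewhat more AEs will have to be recorded.
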